CRF	Case report form
CRC	Clinical research coordinator
CRA	Clinical research associate

Protocol Summary

Study title: Endovascular treatment with or without intravenous thrombolysis in acute ischemic stroke due to basilar artery occlusion: A multicentre, prospective, randomized controlled trial.

Rationale: It is well-established that both intravenous thrombolysis (IVT) and endovascular treatment (EVT), including stent retrievers and aspiration thrombectomy, are safe and effective in treating acute ischemic stroke (AIS) caused by basilar artery occlusion (BAO) within 4.5 hours of symptom onset in selected patients. Currently, both IVT followed by EVT and EVT alone are widely used for the treatment of AIS-BAO, but no direct comparison of their efficacy and safety was reported. Only a limited number of cohort and registry studies have preliminarily compared the two strategies in the treatment of AIS-BAO, with results generally indicating that IVT followed by EVT was slightly superior to EVT alone. However, these findings are generally limited by small sample sizes, heterogeneous inclusion and exclusion criteria, different endpoint definitions, and distinct study designs, leading to inconsistent conclusions.

Objective: To assess the efficacy and safety of IVT followed by EVT and EVT alone in the treatment of patients with AIS-BAO who are eligible for both treatment strategies within 4.5 hours of symptom onset.

Study design: This is a multicentre, prospective, open-label, blinded endpoint evaluation, randomized controlled trial (PROBE design). Based on previous observational studies, this trial primarily aims to validate the superiority of IVT followed by EVT over EVT alone. However, given the limited prior data and evidence from the anterior circulation, this trial will also investigate the non-inferiority of EVT alone comparing with IVT followed by EVT in case the two strategies demonstrate similar efficacy. An interim analysis will be conducted when 1/3 of the sample size (114 patients) has completed primary endpoint follow-up. The interim analysis will focus on sample size re-estimation based on conditional power calculated by the data and safety monitoring board (DSMB), which will provide recommendations on whether to adjust the sample size.

Inclusion criteria:

1. A clinical diagnosis of AIS.
2. Caused by BAO confirmed by CTA, MRA, or DSA. (BAO is defined as the absence of visualization of the basilar artery on CTA, MRA or DSA. Bilateral vertebral artery occlusions or occlusion of a unilateral vertebral artery that is the sole supplier of the basilar artery, even in the presence of patent basilar artery, will be considered de facto BAO.)
3. CT or MRI ruling out intracranial hemorrhage,
4. Eligible for IVT and EVT (within 4.5 hours of symptom onset). (Symptoms onset is defined as point in time the patient was last seen well [at baseline] if patients are unable to provide a reliable history or the point in time when symptoms have started if patients can provide a reliable history. Symptoms onset includes diplopia, midline ataxia, visual loss, sensory or motor deficits, and conscious disturbance. Isolated vertigo [not accompanied by dysarthria, motor weakness, sensory symptoms, double vision, depressed level of consciousness] is not considered onset of symptoms.)
5. NIHSS score ≥ 6 .
6. Age ≥ 18 years.
7. Signed informed consent by the patient or legal representative.

Exclusion criteria:

1. mRS score > 2 before this stroke.
2. Any contraindication to IVT as per the 2019 AHA/ASA guidelines for early management of AIS:

- (1) Blood pressure > 185/110 mmHg and cannot be controlled by standard medication,
 - (2) Blood glucose < 50mg/dL (2.8 mmol/L) or > 400mg/dL (22.2 mmol/L),
 - (3) Had a cerebral infarction in the previous 6 weeks with residual neurological deficit or signs of recent infarction on neuroimaging,
 - (4) Severe head trauma in the previous 3 months,
 - (5) Major surgery or severe trauma in the previous 2 weeks,
 - (6) Gastrointestinal or urinary bleeding in the previous 3 weeks,
 - (7) previous intracranial hemorrhage,
 - (8) Using anticoagulants and INR > 1.7,
 - (9) Known platelet count < $100 \times 10^9/L$,
 - (10) treatment with direct thrombin or factor X inhibitors,
 - (11) Heparin treatment in the previous 48 hours with the APTT exceeding the upper limit of normal.
3. Pregnancy, breastfeeding, or intention to conceive during the study period.
 4. Other conditions deemed unsuitable by the investigator.

Intervention: In accordance with the 2019 AHA/ASA guidelines for early management of AIS and recommendations from the steering committee (SC): In EVT alone group, EVT will be performed as quickly as possible. In IVT followed by EVT group, patients will receive IVT with alteplase (0.9 mg/kg, maximum 90 mg in one hour) before EVT. Efforts will be made to minimize delays in EVT initiation due to IVT administration. EVT techniques include retrievable stent thrombectomy, thrombus aspiration, balloon angioplasty, stent implantation, or combinations thereof. The specific EVT approach will be at the discretion of the treatment team.

Primary endpoint: The primary endpoint of the study is the proportion of patients achieving mRS ≤ 2 at 90±14 days after stroke onset. The proportion of patients achieving the primary endpoint will be calculated for each group, along with the rate difference (RD) and its 95% confidence interval (CI). A log-binomial model with a log-link function will be used to adjust the rate difference for multiple covariates, including age, pre-stroke mRS, time from onset to randomization, stroke severity (baseline NIHSS), and collateral circulation status (baseline PC-CS). The adjusted RD and its 95% CI will be reported.

Secondary endpoints:

1. Proportions of patients with mRS = 0 or 1 and mRS = 0–3, and mRS score at 90±14 days after stroke onset.
2. NIHSS score at 18–24 hours after procedure, 24–74 hours after procedure, and 5–7 days after stroke onset and their changes from baseline.
3. Proportions of patients with a NIHSS score = 0 or 1, a NIHSS score = 0–2, a NIHSS score improvement ≥ 4 points, and a NIHSS score improvement ≥ 8 points. at 18–24 hours after procedure, 24–74 hours after procedure, and 5–7 days after stroke onset.
4. GCS score at 18–24 hours after procedure, 24–74 hours after procedure, and 5–7 days after stroke onset and their changes from baseline.
5. BI score and the proportion with BI = 95–100 at 30±7 and 90±14 days after stroke onset.
6. EQ-5D-5L score at 90±14 days after stroke onset.
7. eTICI score and successful reperfusion rates before and after EVT.
8. mAOL score and recanalization rates at 24–72 hours after procedure.
9. PC-ASPECTS score at 24–72 hours after procedure.
10. Lesion volume based on quantitative imaging detection at 24–72 hours after procedure and 5–7 days after stroke onset.

Safety endpoints:

1. All-cause mortality within 7, 30±7 and 90±14 days after stroke onset.
2. Proportions of patients with intracranial hemorrhage and symptomatic intracranial hemorrhage at 24–72 hours after procedure and 5–7 days after stroke onset.
3. Proportions of patients with embolization to new territory during EVT.
4. Proportions of patients with new cerebral infarction at 24–72 hours after procedure and 5–7 days after stroke onset.
5. EVT procedure-related complications within 90±14 days after stroke onset.
6. Other serious adverse events within 90±14 days after stroke onset.

Sample size and statistical methods: Currently, no large-scale randomized controlled trials (RCTs) exist in this field. Therefore, the calculation of the sample size for this study will be based on the results of the RESCUE-RE registry study conducted in the Chinese population. According to the study, the proportion of patients achieving a mRS score ≤ 2 at 90±14 days post-procedure was 42.03% in the IVT followed by EVT group and 26.14% in the EVT alone group. Based on a superiority hypothesis, this study aims to verify whether the favorable outcome rate in the IVT followed by EVT group is superior to that in the EVT alone group. Assuming a one-sided type I error rate of 0.025 and a statistical power of 80%, with equal allocation between the two groups (1:1), each group will require 136 patients (a total of 272 patients). Considering an anticipated dropout rate of approximately 20%, the final sample size will be adjusted to 340 patients, with 170 patients per group.

This study hypothesizes that IVT followed by EVT is superior to alone EVT. However, given limited reference data and evidence suggesting the non-inferiority of EVT alone in the anterior circulation, an interim analysis will be conducted after one-third (114) of patients have completed follow-up for the primary endpoint. At this stage, the Data and Safety Monitoring Board (DSMB) will perform a sample size re-estimation based on the efficacy data obtained from both groups. Using the available data, the DSMB will calculate the conditional power and provide recommendations to the BEST-BAO research team regarding sample size adjustments or potential modifications to the study hypothesis.

If the efficacy advantage of the IVT followed by EVT group over the EVT alone group is less than anticipated, the sample size may be expanded appropriately, with an upper limit of no more than 20% of the original sample size. If the efficacy of the two groups appears to be similar, the study design will shift to a non-inferiority framework, evaluating whether EVT alone is non-inferior to IVT followed by EVT. Assuming similar efficacy (with both groups achieving a 90-day mRS score ≤ 2 in 42.03% of patients), the current sample size of 170 patients per group provides 80% power to test non-inferiority, with a one-sided type I error rate of 0.025 and a non-inferiority margin of -15% in rate difference. The interim analysis and sample size re-estimation will be conducted under the strict control of the DSMB to ensure that the type I error rate is not inflated.

The primary analysis of this study will follow the intention-to-treat (ITT) principle. The main analysis will be conducted on the modified intention-to-treat (m-ITT) population, defined as all randomized patients who received treatment, analyzed according to their original randomization group. Additional populations, such as the As-Treated Set (ATS) and the Per-Protocol Set (PPS), will be used for sensitivity analyses. Except for the primary efficacy endpoint, which will be tested using a one-sided significance level of 0.025 for superiority or non-inferiority evaluation, all other statistical tests will be conducted using a two-sided significance level. A P-value < 0.05 will be considered statistically significant for these comparisons.

1. Introduction and background

Stroke is a leading cause of death and disability in China, with acute ischemic stroke (AIS) accounting for approximately 85% of all acute strokes. Among these, large vessel occlusion-related AIS (AIS-LVO) represents about 20% of cases^[1]. Posterior circulation infarction, which occur in the vertebrobasilar artery territory, comprise 20–25% of all ischemic strokes. Although less common than anterior circulation ischemic strokes, posterior circulation infarctions—particularly AIS caused by basilar artery occlusion (AIS-BAO)—often present with severe symptoms and poor outcomes. Due to the heterogeneity of initial symptoms and diagnostic challenges, AIS-BAO frequently results in poor prognoses, posing significant challenges in clinical diagnosis and treatment.

The safety and efficacy of intravenous thrombolysis (IVT) with recombinant tissue plasminogen activator (rtPA) within 4.5 hours of symptom onset in AIS have been confirmed by numerous randomized controlled trials (RCTs). However, the heterogeneous presentation of posterior circulation AIS, the difficulty in clinical recognition compared to anterior circulation AIS, and the severe neurological deficits—especially the high mortality rate of AIS-BAO—pose various limitations on IVT. Endovascular treatment (EVT), including thrombectomy techniques, has substantially reduced the mortality and disability rates of patients with AIS-LVO. The key to treating AIS-BAO is recanalizing the acutely occluded basilar artery and rescuing the ischemic penumbra. Large RCTs have demonstrated that early EVT achieves better clinical outcomes in anterior circulation AIS-LVO patients eligible for mechanical thrombectomy compared to IVT alone^[2-8].

In recent years, while multiple large RCTs have confirmed the efficacy of EVT for anterior circulation AIS-LVO, evidence for EVT in posterior circulation AIS-LVO remains limited. The BEST trial enrolled AIS patients with vertebrobasilar artery occlusion within 8 hours of symptom onset to compare EVT plus standard medical treatment versus medical treatment alone. The results showed that the combination group achieved better outcomes at 90 days, with no significant difference in mortality or symptomatic intracranial hemorrhage (sICH) rates compared to the medical treatment-only group^[9]. Similarly, the BASICS trial, an international multicenter RCT, enrolled 300 AIS-BAO patients within 6 hours of symptom onset and compared EVT combined with standard medical treatment to standard medical treatment alone. This study found no significant differences between the two groups in good functional outcomes, sICH, or mortality^[10].

Recently, two studies focusing on thrombectomy for AIS-BAO reported promising results. The BAOCHE study^[11] randomized AIS-BAO patients who presented 6–24 hours after symptom onset into a thrombectomy plus standard medical treatment group or a standard medical treatment-only group. The primary endpoint was the proportion of patients with modified Rankin Scale (mRS) scores of 0–3 at 90 days. A total of 217 patients (110 in the combination group, 107 in the medical treatment group) were enrolled, and the results demonstrated that thrombectomy performed within 6–24 hours led to better functional outcomes at 90 days. The ATTENTION study^[12], another RCT conducted across 36 stroke centers in China, enrolled AIS-BAO patients within 12 hours of symptom onset. Patients were randomized 2:1 to thrombectomy plus optimal medical treatment or optimal medical treatment alone. The primary outcome was the proportion of patients achieving an mRS score of 0–3 at 90 days, and 340 patients (226 in the combination group, 114 in the medical treatment group) were enrolled. The results showed that thrombectomy within 12 hours significantly improved functional outcomes. Both studies demonstrated that thrombectomy combined with medical treatment yielded better outcomes than medical treatment alone for AIS-BAO. However, questions remain regarding the optimal timing, treatment modalities, bridging strategies, and anesthesia options for EVT in posterior circulation AIS. Further exploration is required to rapidly identify posterior circulation strokes and select appropriate EVT strategies based on clinical indications.

Clinically, the morbidity and mortality of posterior circulation AIS-LVO exceed 80%. AIS-BAO, in particular, is a neurological emergency with extremely high mortality if untreated, significantly affecting patients' quality of life and imposing substantial medical and financial burdens on families and society. IVT remains the most effective

ultra-early treatment for AIS within 6 hours of onset. However, the adoption of IVT for posterior circulation AIS is lower than that for anterior circulation AIS, potentially due to delays in diagnosis or missed diagnoses caused by the heterogeneity of AIS-BAO symptoms. Among AIS patients receiving IVT, posterior circulation strokes (PCS) account for about 5–19%. Studies comparing the efficacy and safety of IVT in PCS and anterior circulation strokes (ACS) have found that while the risk of hemorrhagic complications is halved for PCS, functional outcomes are similar, but mortality is higher^[13]. Clinically, IVT can be used as standalone therapy for AIS-BAO or as a prelude to EVT. Which approach better improves AIS-BAO outcomes remains uncertain.

To date, most studies on IVT with EVT have focused on anterior circulation AIS. Both IVT and EVT are time-dependent treatments for AIS, with EVT success hinging on prompt initiation and optimization of processes to reduce door-to-puncture time (DTP). The SKIP trial found no significant difference in the time from randomization to femoral artery puncture between only EVT and IVT with EVT^[14]. Similarly, the DEVT trial, conducted in China, also reported no difference in this time interval between the two groups^[15]. A meta-analysis of 38 observational studies including 11,798 AIS-LVO patients (56% of whom underwent IVT with EVT) also confirmed no significant difference in EVT procedural time between the two groups^[16]. For anterior circulation AIS-LVO, four recent RCTs showed mixed results. DIRECT-MT and DEVT demonstrated that only EVT was non-inferior to IVT with EVT in terms of good functional outcomes at 90 days, while SKIP and MR CLEAN-IV did not confirm non-inferiority. Thus, EVT alone requires further robust evidence^[17, 18]. Regarding safety, all four RCTs confirmed that IVT with EVT does not increase sICH rates^[14, 15, 17, 18]. Additionally, the aforementioned meta-analysis^[16] confirmed that IVT with EVT does not increase sICH risk. SKIP, DIRECT-MT, and DEVT further showed no significant difference in mortality between the two groups^[14, 15, 17]. However, the meta-analysis^[16] suggested that IVT with EVT significantly reduces 90-day mortality compared to only EVT. A real-world study^[19] also found that IVT with EVT was independently associated with lower 90-day mortality compared to only EVT.

Does IVT before EVT achieve higher recanalization rates? A retrospective study^[20] including 93 AIS patients with middle cerebral artery occlusion showed that IVT with EVT resulted in a higher proportion of reperfusion within 1 hour of femoral artery puncture compared to only EVT. Moreover, IVT with EVT achieved significantly higher rates of successful reperfusion (mTICI \geq 2b). The DIRECT-MT study^[17] found that IVT with EVT caused fewer new infarctions from thrombus fragmentation than only EVT. Similarly, post-hoc analyses of the ESCAPE trial^[21] demonstrated that IVT with EVT significantly reduced new infarct risk compared to only EVT. Another study of 57 patients with M1 segment occlusions^[22] reported that IVT with EVT often required fewer thrombectomy passes to achieve recanalization compared to only EVT.

Combination therapy combines the rapidity of IVT with the high recanalization rates of EVT, theoretically offering better outcomes than only EVT. However, most of these studies focus on anterior circulation stroke treatment. To date, no large-scale RCTs have specifically evaluated EVT with or without prior IVT for AIS-BAO. Therefore, we plan to conduct a multicenter, prospective, randomized controlled study to assess the impact of different EVT strategies on outcomes in AIS-BAO.

2. Study objectives

The primary objective of this trial is to compare the efficacy and safety of IVT followed by EVT versus EVT alone in patients with AIS caused by BAO who are eligible for both treatment strategies within 4.5 hours after symptom onset.

The secondary objectives include assessing the effects of the two treatment strategies on neurological function (assessed by National Institutes of Health Stroke Scale [NIHSS] score), activities of daily living (assessed by Barthel Index [BI] score), quality of life (assessed by EQ-5D-5L score), cerebrovascular reperfusion (assessed by

eTICI), cerebrovascular recanalization (assessed by mAOL), infarct size (assessed by PC-ASPECTS and quantitative imaging detection), mortality, and the incidence of symptomatic intracranial hemorrhage (sICH).

3. Study design

This is a multicentre, prospective, open-label, blinded endpoint evaluation, randomized controlled clinical trial (PROBE design). Based on published observational studies, this trial will first validate the superiority of IVT followed by EVT compared with EVT alone. However, given the limited prior evidence and the current findings from anterior circulation stroke studies, this trial will also validate the non-inferiority of EVT compared with IVT followed by EVT alone if the efficacy of the two treatment strategies is found to be comparable.

An interim analysis is scheduled after one-third of the sample size completes follow-up for the primary endpoint. The primary purpose of the interim analysis is to allow for sample size re-estimation. The data and safety monitoring board (DSMB) will calculate the conditional power based on the current data and provide recommendations to the BEST-BAO research team regarding potential sample size adjustments.

The trial will be conducted at nationally recognized stroke centers and is expected to last for 3 years.

4. Study population

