8.1.3 Safety endpoints

The safety endpoints include:

- (1) All-cause mortality within 7, 30±7, and 90±14 days after stroke onset.
- (2) Proportions of patients with intracranial hemorrhage and symptomatic intracranial hemorrhage (**Appendices 9–11**) at 24–72 hours after procedure and 5–7 days after stroke onset.
- (3) Proportions of patients with new regional cerebral embolisms during EVT (**Appendix 12**).
- (4) Proportions of patients with new cerebral infarction at 24–72 hours after procedure and 5–7 days after stroke onset.
- (5) EVT procedure-related complications within 90±14 days after stroke onset.
- (6) Other serious adverse events within 90±14 days after stroke onset.

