
Unless otherwise specified, all statistical tests will be two-sided, with a significance level of 0.05 (two-sided). P-values will be reported to three decimal places, and values less than 0.001 will be reported as "P < 0.001".

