## 3.3 Multiplicity

This study does not involve early termination due to efficacy during interim analysis. Therefore, there are no issues related to multiplicity.

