#### 3.9.2 Secondary efficacy endpoints

The secondary efficacy endpoints are as following:

- (1) Proportions of patients with mRS = 0 or 1 at 90 days after stroke onset.
- (2) Proportions of patients with mRS = 0–3 at 90 days after stroke onset.
- (3) mRS score at 90 days after stroke onset.

(4) NIHSS score at 18–24 hours after procedure, 24–74 hours after procedure, and 5–7 days after stroke onset and their changes from baseline.

(5) Proportions of patients with a NIHSS score = 0 or 1, a NIHSS score = 0–2, a NIHSS score improvement  $\geq 4$  points, and a NIHSS score improvement  $\geq 8$  points at 18–24 hours after procedure, 24–74 hours after procedure, and 5–7 days after stroke onset.

(6) Glasgow coma scale score (GCS) at 18–24 hours after procedure, 24–74 hours after procedure, and 5–7 days after stroke onset and their changes from baseline.

(7) Barthel Index score (BI) and proportions of patients with BI = 95–100 at 30 and 90 days after stroke onset.

(8) EQ-5D-5L score at 90 days after stroke onset.

(9) eTICI score and successful reperfusion rates before and after EVT.

(10) mAOL score and recanalization rates at 24–72 hours after procedure.

(11) PC-ASPECTS score at 24–72 hours after procedure and 5–7 days after stroke onset.

(12) Lesion volume based on quantitative imaging detection at 24–72 hours after procedure and 5–7 days after stroke onset.

For categorical endpoints (1, 2, 5, 7, 9, and 10), proportions will be calculated with 95% CI using the exact Clopper-Pearson method. Group comparisons will use chi-square tests, continuity-corrected chi-square tests, or Fisher's exact test, as appropriate, and P-values will be reported. RD and RR with 95% CIs will also be calculated. Both unadjusted and adjusted results will be reported. Covariates include age, pre-stroke mRS, time from onset to randomization, NIHSS score, and collateral circulation.

For continuous endpoints (4, 6, 7, 8, 11, and 12), group comparisons will use independent samples t-tests (if normality and homogeneity of variance are satisfied) or Wilcoxon rank-sum tests (if not). Mean differences with 95% CIs will also be calculated. Both unadjusted and adjusted results will be reported. Covariates include age, pre-stroke mRS, time from onset to randomization, NIHSS score, and collateral circulation.

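### Any non-primary test with P < 0.05 may be called significant, across about 39 to 42 secondary comparisons with no order, gate or correction

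*Protocol*

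**What the plan says.** The Protocol Summary, under sample size and statistical methods, gives the primary endpoint a one-sided level of 0.025. It then says that "all other statistical tests will be conducted using a two-sided significance level", and that "A P-value < 0.05 will be considered statistically significant for these comparisons". SAP 3.2.2 makes two-sided 0.05 the default for all tests not otherwise specified.

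SAP 3.9.2 lists 12 secondary efficacy items, several of which hold many comparisons. One item begins "Proportions of patients with a NIHSS score = 0 or 1, a NIHSS score = 0–2", adds two improvement thresholds, and applies all four at three visits. For the categorical items the SAP plans chi-square, continuity-corrected or "Fisher's exact test, as appropriate, and P-values will be reported". For the continuous items it plans t-tests or Wilcoxon tests, and for the mRS shift a common odds ratio with its 95% CI. In each case "Both unadjusted and adjusted results will be reported".

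SAP 3.3 is the only section on multiplicity. It notes that the interim analysis cannot stop the trial early for efficacy and concludes: "Therefore, there are no issues related to multiplicity". No section of either document gives a test order, a condition on the primary result, a split of alpha or a correction. None describes the secondary endpoints as exploratory or descriptive.

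**The concern.** Secondary endpoints are often left uncorrected on the understanding that they are supportive. That understanding is not available here, because the plan states the reverse: each non-primary test that reaches P < 0.05 counts as significant in its own right. The reason given in SAP 3.3 deals with repeated looks at one endpoint. It does not deal with one look at many endpoints.

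At stake is how the secondary results can be read. If a handful of several dozen related comparisons fall below 0.05, the plan allows each to be called significant, and a reader would have no agreed way to separate them from chance.

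**Working it through.** **No stated figure to reproduce.** The documents give no familywise error rate for the secondary endpoints. The sample size rests on the primary test alone: (0.4203 × 0.5797 + 0.2614 × 0.7386) × (1.960 + 0.842)² / 0.1589² gives 136 per group, and 272 / 0.8 = 340, as the plan states.

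**Count of comparisons (SAP 2.1.2 and 3.9.2; Protocol 8.1.2 agrees):**

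- mRS 0–1, mRS 0–3, mRS shift: 3
- NIHSS score and change, 3 visits: 6
- four NIHSS proportions, 3 visits: 12
- GCS score and change, 3 visits: 6
- BI score and BI 95–100, 2 visits: 4
- EQ-5D-5L: 1
- eTICI score and reperfusion rate, before and after EVT: 4
- mAOL score and recanalization rate: 2
- PC-ASPECTS, 2 times: 2
- lesion volume, 2 times: 2

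Total: 3 + 6 + 12 + 6 + 4 + 1 + 4 + 2 + 2 + 2 = 42.

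**Other readings.** The Protocol Summary lists PC-ASPECTS only at 24–72 hours, which gives 41. SAP 3.9.2 places the eTICI and mAOL items only among the categorical endpoints. If those scores are not tested apart from their rates, three comparisons drop out (eTICI score before and after, mAOL score): 42 − 3 = 39.

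**Expected false positives with no true effect.** This is 0.05 × k, and correlation does not change it:

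- k = 42: 2.10
- k = 41: 2.05
- k = 39: 1.95

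**Chance of at least one, if independent.** This is 1 − 0.95^k:

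- k = 42: 0.884
- k = 41: 0.878
- k = 39: 0.865

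**Chance of at least one, if correlated.** The documents give no correlations, so a common correlation ρ among 42 normal test statistics is assumed. With c = 1.960, the chance is 1 − ∫ φ(u) [Φ((c − √ρ·u)/√(1 − ρ)) − Φ((−c − √ρ·u)/√(1 − ρ))]^42 du:

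| Assumed ρ | Chance of at least one P < 0.05 |
|---|---|
| 0.3 | 76% |
| 0.5 | 58% |
| 0.7 | 38% |
| 0.9 | 19% |

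**With control in place.** Bonferroni over 42 tests would use 0.05 / 42 = 0.00119 each, with a familywise error of 0.049 under independence. A fixed sequence at two-sided 0.05 also holds the familywise rate at 0.05, without splitting alpha.

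**Outside the count.** The safety comparisons in SAP 3.10 fall under the same rule. The 14 subgroup factors in SAP 3.9.3 have no multiplicity rule either.

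**The case against.** The strongest reply is that the plan's conclusions rest on the primary endpoint. Success criteria exist only for the adjusted risk difference (SAP 3.9.1), the sample size is set only for it, and Protocol 13.6 directs the manuscript to the primary research questions. This stands in part. A reader might infer that a stray secondary result is meant to carry the report if the primary fails. The documents do not plan that; they only leave it open.

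A reader might also infer that the list multiplies further, through adjusted and unadjusted versions on three analysis sets. The documents do not support counting this way. SAP 3.9.2 expressly assigns P-values only to the unadjusted categorical tests. SAP 3.9 names the as-treated and per-protocol sets as sensitivity analyses, which re-examine the same hypotheses.

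A third inference is that chance findings are likely. The endpoints overlap heavily, so the independence figure is an upper value. In the correlated model the chance is above one half at ρ = 0.5 but below it at 0.7. The expected number of about two does not depend on this.

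Finally, the open-label design adds little here. Clinical and imaging assessors are blinded (Protocol 8.1.5, 8.1.6 and 8.2), and open-label conduct is a different matter from multiplicity.

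None of these replies supplies the missing order, gate, correction or label.

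**Conclusion.** The point holds. As written, the plan lets any of about 39 to 42 secondary comparisons be called significant at two-sided 0.05, and the reason in SAP 3.3 does not cover them. With no true effect, about two false positives are expected. The chance of at least one is at most about 88% (independence) and about 76% to 19% for an assumed common correlation of 0.3 to 0.9, always well above 5%.

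These figures assume no effect on any secondary endpoint and tests that run at their nominal level. The correlation range is an assumption, not a figure from the documents.

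A reader might take this as a flaw in the primary test. It is not: the primary type I error is not affected by this point. The lack of a lead definition among the three for symptomatic intracranial hemorrhage (Protocol Appendices 9–11) is a separate matter and plays no part in the count.

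**What to change.** Before unblinding, replace three statements: the P < 0.05 sentence in the Protocol Summary, the conclusion in SAP 3.3, and the SAP 3.2.2 default as it applies to secondary, safety and subgroup analyses. State instead that these analyses are supportive and are reported as estimates with 95% CIs, without claims of statistical significance.

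If the sponsor wants confirmatory secondary claims, pre-specify a short fixed sequence on the m-ITT set with covariate adjustment. One example is the mRS shift, then mRS 0–3, then mRS 0–1; the order is the sponsor's choice. Test each at two-sided 0.05, begin only after the primary superiority test succeeds, and stop at the first failure. Because the trial may switch framework at the interim analysis, also state that under non-inferiority the secondary endpoints are descriptive unless a separate gate is defined.

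The cost is a wording change to both documents. No extra patients are needed and primary power is unchanged. The sponsor gives up calling isolated secondary P-values significant.
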